15. PLANNED INTERIM ANALYSIS

An interim analysis for futility will be performed once 50% of patients (the first 150 patients) have completed 12-week assessments during the double-blind study period or have withdrawn from the study early. The futility will be assessed using conditional power (CP). The study may be terminated if the CP is less than 25%. An independent statistician from a third party will perform the analysis.

15.1. Statistical Methods

The independent statistician may consider using the normal distribution based z-test as an approximation to calculate the CP for the interim analysis. Using the z-test approximation, the CP calculation can be simplified as:

$$CP(n, N, \alpha) = 1 - \Phi \left(c(z_{1-\alpha/2} - \frac{n\Delta_1 + (N-n)\Delta}{\sqrt{2n\sigma_1^2 + 2(N-n)\sigma^2}}) \right)$$

$$\text{Where } c = \sqrt{\frac{n * \sigma_1^2 + (N - n) * \sigma^2}{(N - n)\sigma^2}}$$

$Z_{1-\alpha/2}$ is the critical value from the standard normal distribution; N is the total number of patients planned for each treatment group and n is the number of patients in each treatment group at interim analysis. Δ_1 and σ_1 are the observed treatment difference and common SD in the interim analysis, respectively. Δ and σ are the unknown treatment difference and common SD of the future data, respectively.

Under the condition of $n=N-n$, $\Delta=\Delta_1$ and $\sigma=\sigma_1$ the CP can be determined by the effect size Δ/σ as

$$CP(n, N, \alpha) = 1 - \Phi \left(\sqrt{2}(z_{1-\alpha/2} - \frac{n\Delta_1 + (N-n)\Delta}{\sqrt{2n\sigma_1^2 + 2(N-n)\sigma^2}}) \right)$$

$$CP(n, N, \alpha) = 1 - \Phi \left(\sqrt{2}(z_{1-\alpha/2} - \sqrt{n} \frac{\Delta_1}{\sigma_1}) \right)$$

The critical variable for the interim analysis is the primary efficacy variable in this study: mean change from baseline in the monthly average number of CH attacks during the 12-week period after administration of the IMP. Observed treatment difference and SD and will be calculated using ANOVA.

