2.4. Sample Size and Power Considerations

A sample size of 258 patients (86 evaluable patients completing the study per treatment group) will provide at least 90% power to detect a treatment difference of 4 CH attacks in the monthly average (assuming a common standard deviation [SD] of 8 CH attacks) at a 2-sided alpha level of 0.05. Assuming a 14% discontinuation rate, approximately 300 patients will be randomized in the trial.

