5.3. Demographics and Baseline Characteristics

The demographic data will be collected at the screening visit after the patient signs the informed consent form. Patient's demographics data including age, age group (<40 years or ≥40 years), gender, race, race group (white or other), ethnicity, region (US/Canada or other), baseline weight (kg), baseline height (cm), and baseline body mass index (kg/m²) will be summarized using descriptive statistics for all analysis sets. For continuous variables, treatment groups will be compared using an analysis of variance (ANOVA) with treatment group as a factor. For categorical variables, treatment groups will be compared using a Pearson's chi-square (or Fisher's exact test if cell sizes are too small).

Baseline characteristics including years since first CCH diagnosis, preventive medication use (yes or no) at screening or baseline, use of any triptans/ergots during the run-in period (yes or no), and number of CH attacks during the run-in period will be summarized for the ITT analysis set using descriptive statistics. No inferential analyses will be performed.

The years since first CCH diagnosis will be calculated as (date of informed consent - first date of CCH diagnosis + 1)/365.25. Rules for handling partial CCH diagnosis date are in Section 4.4.

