6.2.2. Primary Efficacy Analysis

The hypothesis testing for the primary analysis is:

$$H_o : \delta_1 = \delta_2 \quad \text{vs} \quad H_a : \delta_1 \neq \delta_2$$

where δ_1 and δ_2 are the estimates of mean change from baseline in the monthly average number of CH attacks for the fremanezumab treatment group and the placebo group, respectively. To control overall type I error rate, the comparison of each active treatment group (fremanezumab 900-mg iv loading dose group and fremanezumab 675-mg sc loading dose group) versus the placebo will be tested using Hochberg's step-up method as described in Section 7.

The primary endpoint will be analyzed using an ANCOVA method. The model will include baseline preventive medication use (yes or no), gender, region (US/Canada or other), and treatment as fixed effects; the baseline number of CH attacks as a covariate. The least square (LS) mean and SE for each treatment group, LS means and corresponding 95% confidence intervals for the treatment differences (fremanezumab - placebo), and associated p-values will be presented.

The analysis will be performed on the FAS and PP analysis sets.

Example SAS code for ANCOVA

```
PROC MIXED DATA=<name>;
  CLASS TRTP SEX REGION BPMU;
  MODEL CHG= BASE BPMU SEX REGION TRTP /S ;
  LSMEANS TRTP /DIFF=CONTROL(("Placebo")) CL ALPHA=0.05;
  ODS OUTPUT LSMEANS= <name> DIFFS= < name> ;
RUN;
```

Where TRTP denotes the planned treatment group; BPMU denotes the baseline preventive medication use (yes or no); CHG denotes the change from baseline; and BASE denotes the baseline number of CH attacks. In bold are the SAS key words.

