15.2. Timing and Data

The interim analysis will be performed once 50% of patients (the first 150 patients, 50 patients per treatment group) have completed 12-week assessments or withdrawn from study early.

Data for the interim analysis futility will be 100% clean. Analysis dataset(s) for CH attacks will be provided to the independent statistician.

The Teva statistician will request to have a copy of the randomization code sent to the independent statistician prior to the interim analysis while all persons who are involved in the study will remain blinded. The production and execution of the analysis and the randomization code will be conducted and kept in a secure location by the independent statistician.

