15.4. Decision Rules

Decision of whether or not to continue the study will be based on CPs from the 2 comparisons (fremanezumab 900-mg iv loading dose group versus placebo or fremanezumab 675-mg sc loading dose group versus placebo).

If both comparisons satisfy the stopping criterion ($CP < 25\%$), this study may be considered to be terminated.

If the CP for 1 of the 2 comparisons is $\geq 25\%$, the study will continue without changes.

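### The futility conditional power uses an unadjusted ANOVA, but the final test it should forecast is a baseline-adjusted ANCOVA

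*SAP*

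**What the plan says.** SAP Section 15.1 names the primary efficacy variable as the interim variable and gives a CP formula driven by the observed difference (Delta_1) and common SD (sigma_1). On their source it says only: "Observed treatment difference and SD and will be calculated using ANOVA". It lists no model terms and gives no reason for the choice. Protocol Section 9.15 specifies no interim method.

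For the final test, SAP Section 6.2.2 says: "The primary endpoint will be analyzed using an ANCOVA method". That model has "the baseline number of CH attacks as a covariate", with treatment, preventive medication use, gender and region as fixed effects.

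The SAP uses the two terms separately. In Section 5.3, for example, "treatment groups will be compared using an analysis of variance (ANOVA) with treatment group as a factor".

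The decision rule is in Section 15: "The study may be terminated if the CP is less than 25" percent. Section 15.4 makes stopping an option only when both dose comparisons meet that criterion. Section 15.3 limits the interim report to a yes/no flag for each active arm.

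**The concern.** Conditional power is meant to be the chance that the planned final test succeeds, given the data so far. The simplified formula in Section 15.1 also uses sigma_1 as the SD of the data still to come. An SD that ignores baseline therefore forecasts an analysis that will not be run.

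The ANOVA difference is unbiased for the same treatment effect. It is more variable, though, because chance baseline imbalance stays in it, and its SD is generally larger than the ANCOVA residual SD. Both features raise the chance that an effective dose falls below 25%.

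CP is the only statistic behind the futility decision. The trial has no Data Monitoring Committee, and only the binary flags are reported. Nobody reading the result would see that a flag came from the noisier model.

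**Working it through.** **Inputs from the documents.** Difference 4, SD 8, two-sided alpha 0.05, 86 evaluable per arm (SAP 2.4); about 300 randomized 1:1:1, so N = 100 per arm; n = 50 per arm at the interim (SAP 15.2); CP threshold 25%.

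**The plan's own figure.** Power at 86 per arm = Phi(4 / (8 x sqrt(2/86)) - 1.960) = 90.6%, and 258 / 0.86 = 300. Both reproduce.

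**The CP rule as a cut-off.** With n = N - n = 50, the SAP formula is CP = 1 - Phi(sqrt(2) x (1.960 - sqrt(50) x Delta_1/sigma_1)). CP < 0.25 requires sqrt(50) x Delta_1/sigma_1 < 1.960 - 0.6745/sqrt(2) = 1.483. The interim Z is sqrt(50/2) x Delta_1/sigma_1, so the rule is Z < 1.483/sqrt(2) = 1.049, an observed effect size below 0.210.

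**Link between the two SDs.** Assume equal baseline and on-treatment variances with correlation rho. The variance of change is 2 x sigma^2 x (1 - rho), and the ANCOVA residual variance is sigma^2 x (1 - rho^2). Hence residual SD / SD of change = sqrt((1 + rho)/2), which is 0.806, 0.866, 0.922 and 0.975 at rho = 0.3, 0.5, 0.7 and 0.9.

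**Assumptions not in the documents.** The value of rho, and whether 8 is the SD of change (reading 1) or the residual SD (reading 2). SAP 2.4 says only "assuming a common standard deviation [SD] of 8 CH attacks", and the power check gives the same 90.6% under either reading.

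**Flag probabilities.** For one arm, Phi(1.049 - E[Z]), where E[Z] = 4/(SD x sqrt(2/50)), which is 2.5 at SD 8. For both arms, bivariate normal with correlation 0.5 because placebo is shared.

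| P(both doses below 25%) | ANOVA | ANCOVA |
|---|---|---|
| *rho order* | *0.3 / 0.5 / 0.7 / 0.9* | *0.3 / 0.5 / 0.7 / 0.9* |
| Reading 1, both doses work | 2.1% | 0.3 / 0.7 / 1.2 / 1.8% |
| Reading 1, one dose works | 7.2% | 2.0 / 3.3 / 4.8 / 6.4% |
| Reading 2, both doses work | 6.7 / 4.8 / 3.4 / 2.5% | 2.1% |
| Reading 2, one dose works | 16.3 / 13.0 / 10.3 / 8.1% | 7.2% |
| Both doses exactly null | 76.2% | 76.2% |

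As rho goes from 0.3 to 0.9, mean CP for an effective dose is 84% (ANOVA) against 94% down to 85% (ANCOVA) under reading 1, and 71% up to 83% against 84% under reading 2.

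**Check by fitting the models.** A three-arm interim was simulated under reading 1 with rho = 0.5 and fitted both ways (20,000 runs). A given effective arm was flagged 7.5% (ANOVA) v 3.5% (ANCOVA), and both arms 2.2% v 0.8%. Under the null (8,000 runs), both arms were flagged about 76% of the time by either method. When baseline is unrelated to change, the degrees of freedom spent on it cost about 0.1 point.

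**Effect on the whole trial if the rule is obeyed.** 20,000 simulated trials per scenario, 100 per arm, no dropout, ANCOVA with Hochberg at the end. Probability of at least one significant dose, ANOVA rule v ANCOVA rule:

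| Scenario | rho 0.3 | rho 0.5 | rho 0.7 | rho 0.9 |
|---|---|---|---|---|
| Reading 1, both work | 97.6 v 99.5% | 97.5 v 98.9% | 96.7 v 97.7% | 96.3 v 96.6% |
| Reading 1, one works | 92.1 v 97.0% | 90.9 v 94.7% | 89.6 v 91.7% | 87.8 v 88.5% |
| Reading 2, both work | 91.6 v 95.8% | 93.2 v 95.8% | 94.3 v 95.4% | 95.5 v 95.8% |
| Reading 2, one works | 79.3 v 87.0% | 82.1 v 86.9% | 84.5 v 86.9% | 86.3 v 87.0% |

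**The case against.** Section 15.1 presents the calculation as an approximation that the independent statistician may consider using, and an unadjusted difference and SD suit that spirit. The rule is permissive and bites only "If both comparisons satisfy the stopping criterion". Under reading 1 the chance of wrongly flagging both effective doses is already only 2.1%. The size of any gain depends on a correlation the documents do not supply. The whole-trial simulation ignores the planned 14% discontinuation. The ANOVA factors are not listed, so the missing baseline term is inferred from the word itself.

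Much of this stands as a limit on size. At rho = 0.9 under reading 1, the saving is about 0.3 points when both doses work and 0.8 when one does. A further limit is that ANCOVA leaves stopping unchanged only at exactly zero effect. With both doses at a difference of 1 attack (reading 1), both-dose flags fall from 51% to between 45% and 51%, although final power per dose is only about 15% to 19%. A more precise test stops weak doses somewhat less often.

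None of this supports keeping the mismatch. Calling the z-test an approximation does not explain feeding it estimates from a different model. Fewer evaluable patients do not remove the gain: at 43 per arm, reading 1 and rho = 0.5, both-dose flags fall from 3.3% to 1.3%. If an adjusted model was intended, the same edit removes the ambiguity.

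**Conclusion.** The concern holds. The interim CP and the final test use different models for the same variable, no reason is given, and the mismatch makes CP too low on average for an effective dose. For correlations of 0.3 to 0.9, ANCOVA lowers the chance that both doses are flagged by about 0.3 to 4.6 points when both work, and by about 0.8 to 9.1 points when one works, across the two readings of the SD. If the rule is followed, the chance of at least one significant dose rises by roughly 0.3 to 4.2 points (both work) or 0.7 to 7.7 points (one works).

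These figures rest on assumed correlations, equal variances, normal data and a true difference of 4. The gain shrinks as the correlation rises and vanishes at slope 1. Type I error is not affected. The change should be made as a low-cost improvement; the trial is valid without it.

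**What to change.** In SAP Section 15.1, replace the ANOVA sentence with one saying that the difference and SD come from the ANCOVA model of Section 6.2.2. Delta_1 is the LS-mean difference and sigma_1 is that model's root mean squared error. State the sign so that benefit is positive: Section 6.2.2 reports fremanezumab minus placebo, where benefit is negative. Keep the CP formula, the 25% threshold and the both-doses rule.

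Section 15.2 now says: "Analysis dataset(s) for CH attacks will be provided to the independent statistician". It should add that the dataset carries baseline attacks, gender, region and preventive medication use. Baseline attacks are already needed to compute change, and the others are collected for the final model. The cost is one replaced sentence and one clarified dataset description.

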15.2. Timing and Data

The interim analysis will be performed once 50% of patients (the first 150 patients, 50 patients per treatment group) have completed 12-week assessments or withdrawn from study early.

Data for the interim analysis futility will be 100% clean. Analysis dataset(s) for CH attacks will be provided to the independent statistician.

The Teva statistician will request to have a copy of the randomization code sent to the independent statistician prior to the interim analysis while all persons who are involved in the study will remain blinded. The production and execution of the analysis and the randomization code will be conducted and kept in a secure location by the independent statistician.

15.3. Result Dissemination

The report of the interim analysis will only include binary results (yes or no) to indicate whether or not the CP for an active treatment group is less than 25%.

15.4. Decision Rules

Decision of whether or not to continue the study will be based on CPs from the 2 comparisons (fremanezumab 900-mg iv loading dose group versus placebo or fremanezumab 675-mg sc loading dose group versus placebo).

If both comparisons satisfy the stopping criterion ($CP < 25\%$), this study may be considered to be terminated.

If the CP for 1 of the 2 comparisons is $\geq 25\%$, the study will continue without changes.

16. STATISTICAL SOFTWARE

All data listings, summaries, and statistical analyses will be generated using SAS[®].

**17. CHANGES TO ANALYSES SPECIFIED IN THE STUDY
PROTOCOL**

None.

APPENDIX A. E-DIARY QUESTIONNAIRE

The recording window on e-diary device is “Yesterday morning 6:00 AM to today at 5:59 AM” or “The day before yesterday morning 6:00 AM to yesterday at 5:59 AM”. A maximum of 48 hours of recall time will be accepted.		
A1	Did you have any Headache?	
A2	How many episodes of headache did you have?	NUMBER
Questions to be asked for each attack		
B1	At what approximate time did the attack begin?	TIME
B2	At what approximate time did the attack end?	TIME
B3	How bad was your headache (head pain) when it was at its worst	MILD MODERATE SEVERE VERY SEVERE
B4	Was the headache restricted to one side of your head?	Yes, my headache was restricted to the left side of my head Yes, my headache was restricted to the right side of my head No, my headache happened in both sides
During any time of your headache, did you experience the following in the same side of you headache?		
B5	Red eye and/or tearing (lacrimation)?	
B6	Stuffy nose (nasal congestion) and/or runny nose?	
B7	Swelling around your eyes (eyelid or palpabrea edema)?	
B8	Sweating on your forehead or face?	
B9	Did your forehead or face become red (flushing)?	
B10	Sensation of full ear (fullness of your ear)?	
B11	Dropping of the upper eyelid (ptosis)	
B12	On the side of pain, your pupil became smaller than on the other side (miosis)?	
B13	Did you become agitated or restless (walking around the room, bending your head, etc.)?	
B14	Did you use oxygen at any time during the attack?	
B15	Did you take any medications during the attack?	GO MED CHEST
Comparing this attack with typical attacks that you experienced BEFORE THIS STUDY, would you say that:		

[figure not shown]
C1	The severity of this attack was	SAME as before study MORE SEVERE than before study LESS SEVERE than before study
C2	The duration of this attack was	SAME as before study LONGER than before study SHORTER than before study
D1	How many hours did you sleep?	NUMBER
D2	How rested/recovered did you feel when you wake up?	Totally rested Somewhat rested; not rested at all
D3	How much time did you have trouble concentrating on activities that you needed to do?	NONE OF THE TIME SOME OF THE TIME MOST OF THE TIME ALL TIME
D4	How interested (motivated, energized) were you in doing daily activities?	VERY INTERESTED SOMEWHAT INTERESTED NOT INTERESTED
	In general how was your day?	It was a good day Neutral (not good or bad) It was a bad day
D5	Which of the following situations best describe your work/school performance, when you did not have a headache? (select only one)	I worked/studied normally My working/studying ability was impaired by less than 50% My work/studying ability was impaired by 50% or more I missed work/school
D6	During your work or school day, approximately how much of the time did you feel that you were working more slowly or taking longer to complete tasks than usual or expected? (select only one)	None of the time Some of the time About half of the time or more
D7	On average, how much of the time were you very tired, asleep, or feeling drained? (select only one)	None of the time Some of the time Most of the time All of the time

[figure not shown]
D8	Which of the following situations best describe your ability to perform household chores, when you did not have a headache? (select only one)	I performed household activities normally My ability to perform household chores was impaired by less than 50% My ability to perform household chores was impaired by 50% or more I could not perform household chores Not applicable
D9	How engaged were you with your partner's or children's activities, when you didn't have a headache? (select only one)	Very engaged Somewhat engaged Not engaged Not applicable

APPENDIX B. LOGICS FOR CLUSTER HEADACHE DERIVATION

[figure not shown]
CLUSTER HEADACHE ATTACK	
OPTION 1	
A1	YES
B3	SEVERE, VERY SEVERE
B4	RESTRICTED TO LEFT OR RIGHT
AND	
{ B5-B12 }	YES TO AT LEAST ONE
OR	
{ B13 }	YES
OPTION 2	
A1	YES
B3	MILD, MODERATE, SEVERE, VERY SEVERE
B4	RESTRICTED TO LEFT OR RIGHT
AND	
{ B14 }	YES
OR	
{ B15 }	YES TO USE OF ACUTE MEDICATION (TRIPTAN OR ERGOT OR OPIOIDS OR BUTALBITAL)
AND	
{ B5-B12 }	YES TO AT LEAST ONE
OR	
{ B13 }	YES

[figure not shown]
APPENDIX C. EUROQOL-5 DIMENSION QUESTIONNAIRE (EQ-5D)

[figure not shown]

[figure not shown]
**APPENDIX D. HOSPITAL ANXIETY AND DEPRESSION SCALE
(HADS)**

[figure not shown]

[figure not shown]
APPENDIX E. 12-ITEM SHORT-FORM HEALTH SURVEY (SF-12)

[figure not shown]

**APPENDIX F. IMPACT ON PARTNER AND FAMILY
QUESTIONNAIRE - PATIENTS**

**APPENDIX G. IMPACT ON PARTNER AND FAMILY
QUESTIONNAIRE - PARTNERS**

**APPENDIX H. WORK PRODUCTIVITY AND ACTIVITY IMPAIRMENT
QUESTIONNAIRE: GENERAL HEALTH V2.0(WPAI:GH)**
